4.4.2. Key Secondary Efficacy Analyses Subject to Type 1 Error Rate Control

Table GPHN.4.2. Secondary Measures Controlled for Type 1 Error

Objectives	Relative to the efficacy measure:	Analysis conducted in a manner similar to	Additional Information
Tirzepatide MTD QW is superior to placebo:	Mean change in body weight (kg) from randomization (Week 36) to Week 88	For treatment regimen estimand: ANCOVA model described in Section 4.3.2.1. For efficacy estimand: MMRM model described in Section 4.3.2.2.	LSM estimates will be plotted by treatment through 88 weeks.
	Mean change in waist circumference (cm) from randomization (Week 36) to Week 88	For treatment regimen estimand: ANCOVA model with terms of treatment group, stratification factors, and corresponding value at randomization (Week 36) as covariates. For efficacy estimand: MMRM model with treatment group, visit, treatment-by-visit interaction, all stratification factors as fixed effects, and corresponding value at randomization (Week 36) as covariates.	LSM estimates will be plotted by treatment through 88 weeks. Refer to Sections 4.3.2.1 and 4.3.2.2 for analysis approach detail.
	Percentage of participants who maintain $\geq 80\%$ of the body weight lost during the 36 weeks of open-label period	For both treatment regimen and efficacy estimand: Logistic regression model will be conducted.	Refer to Section 4.4.1 for analysis approach detail.
Tirzepatide MTD QW is superior to placebo:	Percentage of study participants who achieve $\geq 5/10/15/20\%$ body weight reduction from Visit 2 (Week 0) to Week 88	For both treatment regimen and efficacy estimand: Logistic regression model will be used.	Refer to Section 4.4.1 for analysis approach detail.
	Time (in weeks), during the 52-week double-blind treatment period, to first occurrence of participants returning to $>95\%$ baseline weight for those who have already lost $\geq 5\%$ since Week 0	For both treatment regimen and efficacy estimand: Cox-proportional hazards model will be used with the terms of treatment group (tirzepatide MTD and placebo), country/pooled country, sex, tirzepatide MTD dose at randomization, and weight at randomization (Week 36) and at baseline (Week 0) as covariates.	Only for participants with at least 5% body weight loss during the open-label lead-in period. For treatment regimen estimand: the participant without event will be censored at Week 88.

Objectives	Relative to the efficacy measure:	Analysis conducted in a manner similar to	Additional Information
			For efficacy estimand: the participant without event will be censored at treatment discontinuation time.
Tirzepatide MTD QW is superior to placebo:	Mean percent change in body weight from randomization (Week 36) to Week 64	For treatment regimen estimand: ANCOVA model will be conducted. For efficacy estimand: MMRM model will be conducted.	LSM estimates will be plotted by treatment through 64 weeks. Refer to Section 4.4.1 for analysis approach detail.

Abbreviations: ANCOVA = analysis of covariance; LSM = least squares mean; MTD = maximum tolerated dose; MMRM = mixed model for repeated measures; QW = once-weekly.

Decision will be guided by the 2-sided p-values in each objective subject to type 1 error rate control with details outlined in Section 2.1.

For submission of Study GPHN to the US FDA to support the registration of tirzepatide for chronic weight management, the key secondary efficacy assessment will be guided by the treatment regimen estimand conducted using the same population as for primary analysis. Assessment of key secondary objectives will be conducted with hybrid imputation of missing data (see Section 4.3.2.3).

For other purposes, the assessment of key secondary efficacy objectives will be guided by the efficacy estimand using the same population as for primary analysis.

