1.2. Estimands

1.2.1. Primary Estimand

The primary clinical question of interest is: What is the impact of MTD of tirzepatide (10 mg or 15 mg) QW, compared with placebo, on the maintenance of weight loss after an initial 36-week open-label tirzepatide lead-in treatment period, in study participants who do not have T2DM, and have obesity ($\text{BMI} \geq 30 \text{ kg/m}^2$) or are overweight ($\text{BMI} \geq 27 \text{ kg/m}^2$) with at least 1 weight-related comorbid condition?

For primary disclosure of Study GPHN including submission to the US FDA

The estimand is described by the following attributes:

- Population: patients qualifying for study entry per protocol inclusion/exclusion criteria who reach and tolerate either tirzepatide 10-mg or 15-mg dose at Visit 11(Week 36).
- Endpoint: percent change in body weight from randomization (Week 36) to 88 weeks.
- Treatment condition of interest: tirzepatide MTD versus placebo, regardless of study drug adherence.
- Handling of intercurrent events (ICEs): The ICEs leading to treatment discontinuation for any reason are addressed by the treatment condition of interest attribute and handled by

treatment policy strategy as described in the International Council for Harmonisation (ICH) E9 (R1) Addendum (ICH 2019). Further details can be found in Section 4.3.2.3.

- Population-level summary: difference in mean between treatment conditions.

Rationale for estimand: the primary estimand was requested by US FDA; it aims at reflecting how participants are treated in clinical practice, irrespective to the compliance to planned course of treatment.

This *de facto estimand* is referred as the “treatment regimen” estimand in the latter sections of this document, which is equivalent to the “hybrid” estimand in the protocol.

For all other purposes

The estimand is described by the following attributes:

- Population: patients qualifying for study entry per protocol inclusion/exclusion criteria who reach and tolerate either tirzepatide 10-mg or 15-mg dose at Visit 11(Week 36).
- Endpoint: percent change in body weight from randomization (Week 36) to 88 weeks.
- Treatment condition of interest: tirzepatide MTD versus placebo, excluding data after discontinuation of study drug.
- Handling of ICEs: The ICEs leading to treatment discontinuation for any reason are addressed by the treatment condition of interest attribute and handled by the hypothetical strategy as described in the ICH E9 (R1) Addendum (ICH 2019).

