Unless specified otherwise, for analyses in the double-blind treatment period, baseline is defined as the last nonmissing data collected prior to or at randomization (Week 36); for analyses including data collected in open-label lead-in period, baseline is defined as the last nonmissing data collected prior to or at study enrollment (Week 0).

For some specific safety related parameters, the definition of baseline and postbaseline for double-blind treatment period are specified in [Table GPHN.4.1](#).

The definition of baseline and postbaseline during the open-label lead-in treatment period can be found in [Appendix 4](#).

Table GPHN.4.1. Baseline and Postbaseline Definitions for Safety Outcomes in Double-Blind treatment Period

Analysis Set	Analysis Type	Baseline	Postbaseline
SS	1.1) Treatment-Emergent Adverse Events	Ongoing at the time of the randomization to the double-blind treatment period.	Starts after randomization visit and ends after the whole study period (including off-drug follow-up visit).
SS	1.2) Treatment-Emergent Abnormal Labs ^a , Vital Signs, and ECGs.	Refer to Table GPHN.6.1 for baseline definition.	Postbaseline will be defined as above (1.1). All scheduled and unscheduled measurements will be included.
SS	1.4) Change from Last Baseline to Week xx and to Last Postbaseline for Labs ^a , Vital Signs, and ECGs.	The last scheduled and unscheduled non-missing assessment recorded during the open-label lead-in period.	Postbaseline will be defined as above (1.1). Only scheduled visits will be included. The ED visits are considered scheduled visits.

Abbreviations: ECGs = electrocardiogram; ED = early discontinuation; SS = Safety Analysis Set.

^a Immunogenicity-related analysis is specified in Section [4.6.5.5](#).

For the primary and key secondary efficacy endpoint analyses subject to type 1 error rate control, data for participants with missing values at the 88-week visit (or weight-related measurements at 64-week visit) will be imputed based on the method described in Section [4.3.2.3](#). Otherwise, missing values will not be explicitly imputed except for the parameters with only 1 postbaseline measure during the analysis period per schedule of activity, where LOCF approach will be applied to impute the endpoint when ED measure is available.

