4.3.2. Main Analytical Approach

4.3.2.1. Analysis Related to the Treatment Regimen Estimand

The analysis related to the treatment regimen estimand will be conducted using the FAS.

The analysis for the mean percent change in body weight will be conducted utilizing ANCOVA. The response variable for the ANCOVA model will be percent change in body weight from randomization to Week 88. This model will include terms of treatment group, country/pooled country, sex, tirzepatide MTD dose at randomization, and body weight at randomization (Week 36) as covariates. The ANCOVA analysis will be conducted with multiple imputation of missing data guided by hybrid method at Week 88 (see Section 4.1 and Section 4.3.2.3 for details) and statistical inference over multiple imputation of missing data guided by Rubin (1987).

With the aid of the ANCOVA model, 2-sided 95% CI for mean percent change in body weight from baseline to the 88-week visit between tirzepatide MTD and placebo will be derived.

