4.3.2.3. Hybrid Methods of Imputation

For efficacy analyses relative to the treatment regimen estimand, the intercurrent events and the resulting missing values will be handled as follows:

- **Category 1:** for missing data solely due to an exceptional circumstance, such as a pandemic or natural disaster (after other reasons for missing data are ruled out), considers the missing data as missing at random. The missing data will be imputed using all nonmissing data of the primary outcome measurement from the same treatment arm.
- **Category 2:** for missing data due to all other intercurrent events, it will be imputed based on retrieved dropouts in the same treatment arm, defined as observed primary outcome measurements, from participants in the same treatment group who had their efficacy assessed after early discontinuation of study drug. In cases where there are not enough retrieved dropouts to provide a reliable imputation model (for example, the model implemented by the SAS program does not converge), an alternative multiple imputation method with reference to the placebo group (ie, placebo multiple imputation) will be used.

In cases where placebo multiple imputation method is used for missing data imputation in Category 2 because of not enough retrieved dropouts, the missing data in Category 1 will be imputed using all nonmissing data of the primary outcome measurement from the placebo group.

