4.4. Secondary Endpoint(s) Analysis

4.4.1. Main Analytical Approach for Categorical Outcome Related to Weight Measurement

For both treatment regimen and efficacy estimand, a logistic regression model will be used. For the proportion of patients achieving weight loss target since

- Baseline (Week 0), the following covariates will be included: treatment group, country/pooled country, sex, and tirzepatide MTD dose at randomization, and body weight at randomization (Week 36) and at baseline (Week 0).
- Randomization (Week 36), the following covariates will be included: treatment group, country/pooled country, sex, and tirzepatide MTD dose at randomization (Week 36), and body weight at randomization (Week 36).

For missing data imputation:

- For treatment regimen estimand: missing data will be handled by hybrid imputation of missing body weight at Week 88 (see Section 4.1 and Section 4.3.2.3 for details).

- For efficacy estimand: missing data will be handled by predicted value from MMRM analysis followed by dichotomization. When MMRM is used, variance-covariance structure for within-patient errors will be same as Section 4.3.2.2.

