6.6.8. Missing Data Due to Exceptional Circumstances

For the primary endpoints and key secondary endpoints, missing data due to exceptional circumstances will be handled as described in Section 4.1 and Section 4.3.2.3.

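### Does the SAP leave it open whether imputed weights count as events in the time-to-regain analysis (H5) under the treatment-regimen estimand?

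*SAP*

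**What the plan says.** Table GPHN.4.2 in SAP 4.4.2 gives H5 a Cox model, limited to participants with at least 5% loss in the lead-in. Its censoring rule is: "For treatment regimen estimand: the participant without event will be censored at Week 88". Under the efficacy estimand, censoring is at treatment discontinuation instead.

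Three general statements also cover H5:

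- Below the table, for the FDA submission: "Assessment of key secondary objectives will be conducted with hybrid imputation of missing data".
- SAP 4.1, for the primary and the type 1 error-controlled key secondary analyses: "data for participants with missing values at the 88-week visit (or weight-related measurements at 64-week visit) will be imputed", by the method of SAP 4.3.2.3.
- SAP 6.6.8, for primary and key secondary endpoints: "missing data due to exceptional circumstances will be handled as described in Section 4.1 and Section 4.3.2.3".

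SAP 1.2.1 handles treatment discontinuation by the "treatment policy strategy as described in the International Council for Harmonisation" addendum, and Table GPHN.1.2 carries this over to the key secondary endpoints. For the responder endpoints, SAP 4.4.1 says "missing data will be handled by hybrid imputation of missing body weight at Week 88". Rubin (1987) is cited for pooling in SAP 4.3.2.1, with the ANCOVA.

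**The concern.** The only rule specific to H5 censors everyone without an event at Week 88, whatever the date of their last weight. No sentence says that an imputed weight above 95% of Week 0 weight is an H5 event, which date it takes, or how log hazard ratios are combined across imputations. Taken alone, the row can be programmed on observed weights. A participant who leaves at Week 45 and is never weighed again would then be event-free to Week 88, which conflicts with treatment policy.

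H5 is alpha-controlled. Under that reading, cumulative regain is understated in both arms. The hazard ratio is biased if tirzepatide stoppers regain after stopping or if dropout differs between arms. With unequal dropout the bias favours the arm that loses more people, and type 1 error can rise.

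**Working it through.** **1. The plan's own figure.** The only power figure is for the primary endpoint (Protocol 9.2, SAP 5): 300 per arm, 25% dropout, difference 6%, SD 8%, 2-sided 0.05. Evaluable per arm: 300 × 0.75 = 225. SE = 8 × √(2/225) = 0.754. 6/0.754 = 7.96, and 7.96 − 1.96 = 6.00, so power exceeds 99.9%. The stated figure of more than 90% holds. No event rate or hazard ratio is given for H5, so every size below rests on assumed rates.

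**2. What an imputed weight can do in H5.** The hybrid method yields a Week 88 value. With x the imputed percent change, the weight is the Week 36 weight × (1 + x/100), compared with 0.95 × Week 0 weight. For someone at 85% of Week 0 weight at Week 36, the threshold is crossed when x exceeds 95/85 − 1 = 11.8%. A weight has no other route into this endpoint. If imputed weights did not decide event status, the imputation sentences in SAP 4.1 and 4.4.2 would do nothing for H5. Once Week 88 is imputed, every participant without an earlier event has a Week 88 status, so censoring the rest at Week 88 is the natural rule.

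**3. Dating.** SAP 4.1 ties imputed values to Weeks 64 and 88, and the endpoint is a first occurrence, so the event takes the date of its visit. Office weights fall at Weeks 40, 52, 64, 76 and 88. A simulation with four pairs of assumed 52-week risks (placebo 20–60%, tirzepatide 5–15%; tirzepatide stoppers at the placebo hazard afterwards) compared dating every unobserved event at Week 88 with dating it at its true visit. The hazard ratios were 0.318 against 0.319, 0.196 against 0.198, 0.387 against 0.391 and 0.187 against 0.192 at 25% dropout per arm. At 15% placebo and 35% tirzepatide dropout the largest gap was 0.011 (0.224 against 0.235). Event status was taken as correctly imputed.

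**4. Pooling.** Rubin's method is the only pooling method that the SAP cites. SAP 4.4.1 does not repeat it for the logistic models, so H5 is no worse specified than the responder endpoints.

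**5. Size if the row were misread.** This weight model uses the plan's 6% and SD 8%, 300 per arm and 1,000 trials. Assumed: mean Week 36 weight 85% of Week 0, and half of stoppers weighed again.

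| Dropout, placebo/tirzepatide | Tirzepatide stoppers | HR, complete data | HR, observed only | HR, imputed counted |
|---|---|---|---|---|
| 25/25 | regain at placebo rate | 0.473 | 0.450 | 0.471 |
| 15/35 | regain at placebo rate | 0.493 | 0.427 | 0.488 |
| 25/25 | unchanged course | 0.413 | 0.418 | 0.416 |

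At 25/25 with regain, 0.450/0.473 = 0.95, about 5% low. Null rejection on observed weights only was 5.3% at 25/25, 5.4% at 20/30, 7.4% at 15/35 and 7.2% at 35/15. The Monte Carlo standard error is √(0.05 × 0.95/1000) = 0.7 points, so the first two do not differ from 5%.

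A harsher hazard model assumes 52-week risks of 45% and 10%, 25% dropout per arm, and tirzepatide stoppers at the placebo hazard.

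| Stoppers weighed at Visit 99 | HR, complete data | HR, observed only | HR, imputed counted |
|---|---|---|---|
| none | 0.262 | 0.180 | 0.260 |
| half | 0.264 | 0.225 | 0.262 |
| three-quarters | 0.264 | 0.244 | 0.263 |

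Under a null of 40% risk in both arms (5,000 trials), rejection on observed weights only was 5.1%, 8.2% and 19.0% at 25/25, 20/30 and 15/35 with no later weights, and 4.6%, 6.6% and 9.8% with half weighed at Visit 99. With imputed events counted it was 4.7–5.5%.

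**The case for a change.** The strongest case for a change is that intent alone does not fix one analysis. Imputation covers two of the five weighing visits, the method in SAP 4.3.2.3 is written for the primary outcome, and the H5 row does not point to it. H5 carries alpha, and the remedy would be a few sentences. With no later weights, the literal reading gives a hazard ratio of 0.180 against 0.262, and up to 19% null rejection.

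The silence of the row stands. The harm does not follow from it, because it needs a programmer to set aside two explicit statements that key secondary analyses use imputed weights. The extreme figures also assume that no stopper is ever weighed again, whereas Protocol 7.1 asks stoppers to attend all visits or return for Visit 99. The 19% further needs a 20-point dropout gap, for which the documents give no support.

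Two further additions could be asked for, and neither earns its place:

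- **Drawing Weeks 64 and 88 jointly within participant.** This would be a new imputation model. In the weight model, separate draws gave a placebo incidence of 28.7% and joint draws 27.7%, against 27.7% true, a gain of one point. Retrieved dropouts at Week 64 may indeed be few: with at least 6 required per arm and visit, the separate-draw model could be fitted in 876 of 1,000 trials. The SAP already has a placebo-based fallback for this: "In cases where there are not enough retrieved dropouts to provide a reliable imputation model".
- **A sensitivity analysis censoring at the last weight.** At 25% dropout per arm it gave 0.235, 0.107, 0.317 and 0.109, against 0.238, 0.110, 0.323 and 0.115 for observed events with censoring at Week 88. The two differ more when dropout is unequal, but last-weight censoring does not count regain after dropout either.

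**Conclusion.** No change is needed. Followed as written, SAP 4.1 and 4.4.2 count imputed Week 64 and Week 88 weights in H5, the visit supplies the date, Rubin's method supplies the pooling, and censoring at Week 88 then agrees with treatment policy. The missing wording is detail that an analyst would fill in this way when programming.

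If the row were nevertheless programmed on observed weights only, the hazard ratio in the model tied to the plan's assumptions would be 0.450 instead of 0.473 at 25% dropout per arm. H5 would be significant in at least 97% of the non-null trials either way. Type 1 error would rise materially only with a large dropout imbalance or with few stoppers weighed again. These sizes rest on assumed event rates, dropout patterns and regain after stopping, none of which the documents give for H5. The models omit the covariates, and the hazard model also omits the 5% loss restriction. The conclusion itself rests on the text, not on these rates.

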4.4.3. Additional Secondary Endpoint(s)

Unless otherwise specified, other secondary efficacy analyses will be guided by the efficacy estimand using the same population as for primary analysis.

Analyses for labs including fasting glucose, hemoglobin A1c, fasting insulin, and lipid parameters will be performed for both SI units and CN units.

4.4.3.1. Additional Secondary Efficacy Analyses

Table GPHN.4.3. Secondary Efficacy Measures Not Controlled for Type 1 Error

Analysis variable	Analysis set	Analysis method	Additional Information
Mean change in measurements of lab tests and vital sign	Data from randomization (Week 36) to Week 88	MMRM model with treatment group, visit, treatment-by-visit interaction, all stratification factors as fixed effects, and the corresponding value at randomization (Week 36) as a covariate	Variance-covariance

Analysis variable	Analysis set	Analysis method	Additional Information
			structure for within-patient errors will be same as Section 4.3.2.2. LSM estimates may be plotted by treatment through 88 weeks. Log transformation will be adopted for fasting insulin and lipid parameters.
Mean change in SF-36 v2 acute form domain score in 
 • Physical Functioning domain (PF) • Role-Physical domain (RP) • Role-Emotional domain (RE) • Mental Health domain (MH) Mean change in IWQOL-Lite-CT Physical Function composite score		ANCOVA model with terms of treatment group, all stratification factors, and the corresponding value at randomization (Week 36) as a covariate.	Missing data will be imputed using LOCF.
Mean change in measurements of lab tests and vital signs	Data from Week 0 to Week 88	MMRM model with treatment group, visit, treatment-by-visit interaction, all stratification factors, and the corresponding value at baseline (Week 0) as covariates.	Variance-covariance structure for within-patient errors will be same as Section 4.3.2.2. LSM estimates may be plotted by treatment through 88 weeks. Log transformation will be adopted for fasting insulin and lipid parameters.
Mean change in body weight, BMI, and percent change in body weight		MMRM model with treatment group, visit, treatment-by-visit interaction, country/pooled country and sex as fixed effects, and the corresponding value at baseline (Week 0) and at randomization (Week 36) as covariates.	Variance-covariance structure for within-patient errors will be same as Section 4.3.2.2. LSM estimates may be plotted by treatment through 88 weeks.

Analysis variable	Analysis set	Analysis method	Additional Information
Mean change in waist circumference		MMRM model with treatment group, visit, treatment-by-visit interaction, all stratification factors as fixed effects, and the corresponding value at baseline (Week 0) as covariates.	Variance-covariance structure for within-patient errors will be same as Section 4.3.2.2. LSM estimates may be plotted by treatment through 88 weeks.
Mean change in SF-36 v2 acute form in 
 Physical Functioning domain (PF) and 
 IWQOL-Lite-CT in 
 Physical Function composite score 		ANCOVA model with terms of treatment group, all stratification factors, and the corresponding value at baseline (Week 0) as covariates.	Missing data will be imputed using LOCF.

Abbreviations: ANCOVA = analysis of covariance; BMI = body mass index; IWQOL-Lite-CT = Impact of Weight on Quality of Life-Lite-Clinical Trials Version; LOCF = last observation carried forward; LSM = least squares mean; MMRM = mixed model for repeated measures; SF-36 v2 acute form = Short Form-36 Version 2 Health Survey acute form.

